3.2 Study Intervention

Once consented, participants will be randomized to receive 0.25mg/kg (up to a maximum

Ketamine 30 min vs 15 min

Version: 7

Date: 06.06.2024

Page 9 of 15

of 30mg) intravenous ketamine mixed with 100cc normal saline (NS) either over: (1) 15-minute slow infusion (SI) or (2) 30-minute slow infusion.

Each group will receive corresponding placebo of 100cc NS for double dummy design.

The group receiving ketamine over 15-minute SI, will also receive 100cc NS over 30 minutes and the group receiving ketamine over 30 min SI will also receive 100cc NS over 15 min. Ketamine/NS placebo infusions will be delivered via infusion pump. The two infusions are to be given simultaneously so that time zero (0) is the same for both infusions.

Ketamine/NS placebo will be prepared and blinded by pharmacy staff and be administered in a blinded fashion by an ED or Research RN. For the purposes of this study a subject will be considered enrolled once they have received any portion of the investigational product.

Patients may not be enrolled in the study more than one time. They may not be re-enrolled if they present to the ED with acute pain a subsequent time. This is to prevent any bias from forming in the data analysis secondary to the side effect profile of the drug as well as the potential psychotropic effect the drug may have.

3.3 Outcomes/Objectives

The primary objective of this study is to attempt to prove that increasing the length of ketamine administration decreases overall incidence and severity of side effects. The side effects to be monitored include fatigue, dizziness, headache, feeling of unreality, hearing, vision, or mood changes, generalized discomfort, and hallucinations. Our goal is to have at least a 20% decrease in overall scores, which equals to a “1” point decrease on the SERSDA scale. SERSDA measures severity of nine adverse effects based on a 5-point scale from “0” (no adverse effect) to “4” (very bothersome effect).

The primary outcome measure of this study is the reduction of the overall side effects as measured by the Side Effect Rating Scale for Dissociative Anesthetics (SERSDA) at 30 minutes.

The secondary objective is to ensure that adequate pain control (VAS ≤ 5 cm) is maintained when ketamine administration is prolonged. To do this we will be measuring pain scores on the 100mm VAS at each protocol specified interval (0, 5, 15, 30, 60 and 90 minutes from the infusion start time, which is defined as time zero). Studies have shown that for clinical significance in pain reduction, there needs to be at least a 13mm difference on the 100mm VAS pain scale.¹⁵

Ketamine 30 min vs 15 min

Version: 7

Date: 06.06.2024

Page 10 of 15

The secondary outcome measure is the severity of self-reported pain on the standard 100mm VAS pain scale (0-100) at 30 minutes.

The need to administer rescue analgesic medication will also be assessed, starting at 30 minutes and again at 60 and 90 minutes post start of the infusion (Time 0).

We will also be monitoring the need for the administration of other interventions to treat ketamine side effects (nausea etc.), as well as vital signs.

The Richmond Agitation Sedation Scale (RASS) (Appendix A) will be used to collect additional data.

Study Schedule

	Time 0 min	Time 5 min	Time 15 min	Time 30 min	Time 60 min	Time 90 min
VITAL SIGNS	X	X	X	X	X	X
SERDSA		X	X	X	X	X
VAS	X	X	X	X	X	X
RASS		X		X		X

4. Data Analysis/Plan

The sample size of n=24 in each study arm (n=48 overall) was determined to detect a clinically significant median change of one unit in the primary outcome and SERDSA scale, for measuring adverse events. This determination assumes the same standard deviation of 1.2 units with 80% power assuming a two-sided alpha type I error rate of 5% used previously to adequately power the Motov study² which was based on the estimated standard deviation from the Andolfatto¹⁶ study. We will enroll stratified by gender (male/female) to ensure equality between the two study groups.

Separate sealed envelopes will be provided to the pharmacist containing the randomization assignment to allow for more comparability between study arms. Each sealed envelope will be identified by gender and patient enrollment number, e.g., 'Male 01', and contain an assignment to either study arm within the envelope. Envelopes for randomized subjects will be stored in the investigational pharmacy. A secondary copy of the randomization assignments will be managed on a secure research shared drive within the Clinical Research Center. Access will be limited to only unblinded study staff. A

Ketamine 30 min vs 15 min

Version: 7

Date: 06.06.2024

Page 11 of 15

maximum enrollment for either gender will be 14 out of the 24 (58.3%) to provide a more balanced gender ratio which is more generalizable to the intended population.

Randomized blocks of 2 and 4 units will be employed within each gender strata to allow for balance across the enrollment period.

Study data will be collected via a REDCap instrument. A randomization number will be assigned and after baseline data is collected, observation and longitudinal data will be captured via a repeated measures survey in REDCap. Time points captured will be baseline (0min), 5min, 15min, 30min, 60min and 90min from the start of the study infusion which is time zero.

Data from this double-blind, double dummy, randomized comparative study will be imported into SPSSv25.0 software (IBM Corp., Armonk, NY) with baseline characteristics summarized by treatment arm. A generalized linear model using an underlying gamma distribution will be employed for all ordinal data including SERDSA outcomes collected at time points before complete resolution to "0". A mixed model regression will be employed for all continuous outcomes across time with missing data assumed to be random. Boxplots of outcome will also be provided at each study time point stratified by study arm. Additionally, the rates of adverse events will be summarized using frequencies and percentages and compared between study arms via Fisher's exact or Pearson chi-square tests depending on cell sample size distribution.

Variables collected during the study include patient demographics (age, sex, pain type/location), vital signs on presentation as well as during specified times (heart rate, blood pressure, respiratory rate, and oxygen saturation), Visual Analogue Scale (VAS) scores, SERSDA scores¹⁷, Richmond Agitation-Sedation Scale (RASS) and time to rescue analgesia.

If patients withdraw from the study prior to medication administration, they will not be included in the final data set. If they decide to withdraw while medication is being administered or after the completion of the infusion, but during the follow-up period of 90 minutes, they will be in the final data set and shown on the diagram as withdrawn.

There may be CITI trained and CRC Credentialed medical students, ED residents and faculty members who will help with the enrollment process and data collection.

Data for this study will be collected in REDCap. REDCap is a HIPAA compliant clinical electronic data capture system. All patient records entered into REDCap will have identifiers removed and will be given a unique study-specific code. Patient identifiers (patient name, DOB, MRN) with codes will be stored separately in an Excel spreadsheet located in a secure folder on the Summa G:/ drive, accessible only to authorized study personnel. Only authorized study personnel will be given access to the data collection sheet in REDCap. Multi-factor authentication (MFA) security is used to access the

Ketamine 30 min vs 15 min

Version: 7

Date: 06.06.2024

Page 12 of 15

REDCap platform. Full audit trails are kept within REDCap.

All study related data will be kept in the CRC for a minimum of 6 years after study completion, unless the study is published. If published, all study data should be kept for 10 years, per Summa policy.

5. Data Safety and Monitoring

Study data will be reviewed for safety and interim analysis will be completed at the following study subject accrual points: 3 patients, 6 patients, 12 patients, 24 patients and 40 patients. The review committee will consist of an odd number of physicians, with a minimum of one physician who is not associated with the Summa Emergency Department. During review, if it is determined the majority of study subjects (75%) did not experience a clinically significant reduction in pain (which is an improvement of 13mm on the 100mm VAS scale) the study will be stopped. The results of each safety monitoring review will be summarized and submitted to the IRB.

CRC staff will be responsible for collecting and communicating AE's, SAE's, UAP's, and protocol deviations per institutional policies.

CRC staff will be responsible for data collection and data entry into REDCap. Data will be reviewed for accuracy and completion on a regular basis.

References:

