Low Dose Ketamine Infusion for Analgesia in the Emergency Department to Reduce Side Effects

Study Protocol and Analysis Plan

NCT05518877

June 6, 2024

Study Title: Low Dose Ketamine Infusion for Analgesia in the ED to Reduce Side Effects: A Double Blind, Double Dummy Randomized Controlled Trial

Principle Investigator: PI: [name], DO
Sub-Investigator: Sub-I: [name]

Address: Summa Health Department of Emergency Medicine
[name]
[name]

1. Purpose of Study

Research has shown low dose ketamine (LDK) Intravenous push (IVP) (0.3mg/kg) to have equivalent pain reduction in moderate to severe acute pain in the Emergency Department (ED) when compared to standard of care of morphine IVP (0.1mg/kg). Ketamine has been shown to produce side effects in these studies, including dizziness, feeling of unreality and mood changes. There were no unexpected side effects or adverse events during this trial.¹ Another study compared IVP with a slower infusion of LDK and showed a decrease in side effects while maintaining similar analgesic efficacy. This trial found increased feelings of unreality for the IVP group (difference of 37.5%) as well as increased rates of sedation.²

In clinical practice, increasing the time/duration of the infusion has resulted in a decrease of reported side effects from patients while still maintaining analgesia. There have been no studies done to prove that there is a further reduction in side effects with a longer LDK infusion. We believe that increasing the infusion time to greater than 15 minutes will reduce the frequency and intensity of expected side effects of ketamine felt by recipients and allow for further use of ketamine as a non-opiate analgesic in the ED.

Overall aims of project:

1. Reduce overall incidence and severity of known side effects of low dose ketamine when given over 30 minutes versus 15 minutes.
2. Maintain adequate pain control, as determined by a Visual Analogue Score (VAS) of ≤ 5 cm (50mm) at 30 minutes after start of ketamine infusion.

Hypothesis: Slow infusion of LDK over 30 minutes will provide adequate pain control (as defined by VAS score of ≤ 5 cm (50mm)), and reduce incidence and severity (by at least 20% or 1 point on Side Effects Rating Scale for Dissociative Anesthetics [SERSDA] scale) of known side effects when compared to LDK given over 15 minutes in moderate to severe acute pain for patients presenting to the ED.

2. Background and Rationale

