A prospective study with 38 patients was conducted to describe the analgesic efficacy and side effect profile of low dose ketamine for acute severe pain in the emergency department (ED). The study trialed a bolus of ketamine (15mg) as intravenous push (IVP) followed by slow infusion (20mg) over 60 min. Patients were offered morphine 4mg as rescue analgesia at the 20-, 40-, and 60-minute marks. Pain was assessed on a 10-point verbal numerical reading scale (NRS), along with vital signs and sedation scores frequently over 120 minutes. At the 60-minute mark, side effect rating scale for dissociative anesthesia (SERSDA) scale was used to assess side effects. Twenty-two patients had clinically significant reduction in pain at 10 minutes. Twenty-five patients had clinically significant reduction at the end of the infusion (60 minutes). Twelve patients did not require or refused adjunct morphine therapy, as pain was adequately controlled throughout the duration of the study. There was a significant proportion of patients that experienced side effects (33 patients, 86%) with a large portion grading them as weak or modest (20 patients, 53%). Thirteen patients (34%) reported side effects as “very bothersome”. The most common side effects were dizziness, fatigue, nausea and feeling of unreality. A large portion of patients (32 patients, 84%) reported they would trial ketamine again for pain management.⁷

A case series looked at 14 patients in an urban ED who received low dose ketamine (0.2-0.4mg/kg) infusions (10-15min) for analgesia. Thirteen patients had received analgesia prior to the ketamine infusion. No patient received rescue analgesia one hour post

infusion. There were no dangerous adverse effects noted. One patient reported tinnitus and uneasiness during the infusion while another reported dizziness.⁸

A recent study conducted in 2017 aimed to show reduction in side effects of LDK by giving it over 15 minutes compared to standard IVP of less than 5 minutes. A total of 48 patients were enrolled and the study showed similar rates of side effects except for overall feeling of unreality, which was significantly higher in IVP group (91.7% vs 54.2%, $p=0.008$). There were similar decreases in pain scores for each group ($p=0.14$) with no significant difference in use of rescue analgesia or change in vital signs.²

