use seems to be due to the side effect profile that is bothersome to some patients. A previous study already showed improvement in side effects, mainly dizziness, when given over a longer period of time (15 minutes). We are hypothesizing that further increasing the administration duration will produce even less side effects while maintaining analgesic properties.

Literature reviews have been done that elaborate on the common side effects of ketamine when given for analgesia. One noted most common events to be nausea, altered mood, psychomimetic effects and headaches when given intravenously for complex regional pain.¹² Another article noted that there seemed to be psychomimetic effects along with hypertension when given for pain control via intravenous infusion, although appeared to improve after infusion was complete.¹³ Similar side effect profile in terms of psychomimetic effects has been seen in other studies and include dizziness, blurred vision, vertigo, nausea/vomiting, dysphasia, nystagmus, nightmares or vivid dreams, impaired motor function and memory deficit but like other studies, improves rapidly after infusion is complete. Cardiovascular effects secondary to the catecholamine release after administration have also been documented. The main effects appear to be tachycardia, hypertension and increase in cardiac output and recommend use of cardiac monitoring but do not seem to be long lasting effects.¹⁴

This study has been determined to be exempt from FDA IND requirements based on all criteria for exemption being met.

3. Study Design

The location of this study will be the Akron City Hospital Emergency Department. The trial will enroll approximately 48 evaluable subjects. An evaluable subject is defined as a subject who completes the entire infusion (30 minutes) and provides a 30 minute VAS and SERSDA score.

This will be an intent to treat prospective, double blind, double-dummy, randomized trial. The primary outcome will be a comparison of side effects of sub dissociative dose ketamine given by slow IV infusion over 15 minutes vs 30 minutes in treatment of moderate to severe acute pain in ED patients. The secondary outcome will be adequate pain control (VAS ≤ 5 cm(50mm)) and need for rescue analgesia between the two groups.

The control group will receive slow IV infusion of ketamine over 15 minutes. The experimental group will receive slow IV infusion of ketamine over 30 minutes.

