APPENDIX A

Visual Analogue Scale (VAS)

Side Effects Rating Scale for Dissociative Anesthetics (SERSDA) Scale

Side Effects	Severity	Scale
Fatigue		0, No Change
Dizziness		1, Weak
Headache		2, Modest
Feeling of Unreality		3, Bothersome
Change in Hearing		4, Very Bothersome
Change in Vision		
Mood Change		
Generalized Discomfort		
Hallucination		

The Richmond Agitation Sedation Scale (RASS)

+4	Combative	violent, immediate danger to staff
+3	Very Agitated	Pulls or removes tube(s) or catheter(s); aggressive
+2	Agitated	Frequent non-purposeful movement, fights ventilator
+1	Restless	Anxious, apprehensive but movements not aggressive or vigorous
0	Alert & calm	
-1	Drowsy	Not fully alert, but has sustained awakening to voice (eye opening & contact \geq 10 sec)
-2	Light sedation	Briefly awakens to voice (eye opening & contact < 10 sec)
-3	Moderate sedation	Movement or eye-opening to voice (but no eye contact)
-4	Deep sedation	No response to voice, but movement or eye opening to physical stimulation
-5	Unarousable	No response to voice or physical stimulation

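### The primary outcome is narrower than the stated aim: nausea, prominent in the protocol's own background, is captured only indirectly, with no scheduled or severity rating

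*Combined protocol and SAP*

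**What the plan says.** Section 1 (Purpose of Study) gives the first aim: "Reduce overall incidence and severity of known side effects of low dose ketamine when given over 30 minutes versus 15 minutes". Section 3.3 repeats this breadth in the primary objective and then ties the outcome to an instrument: "The primary outcome measure of this study is the reduction of the overall side effects as measured by the Side Effect Rating Scale", assessed at 30 minutes. The same section states that "SERSDA measures severity of nine adverse effects based on a 5-point scale" and names the effects to be monitored: "fatigue, dizziness, headache, feeling of unreality, hearing, vision, or mood changes, generalized discomfort, and hallucinations". The form in Appendix A carries the same nine rows.

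The background in section 2 describes a wider set of known effects. On the 38-patient emergency department study of a ketamine push followed by an infusion: "The most common side effects were dizziness, fatigue, nausea and feeling of unreality". On a literature review of intravenous ketamine for complex regional pain: "One noted most common events to be nausea, altered mood, psychomimetic effects and headaches". Nausea is also named among the ketamine-arm effects in the morphine comparison.

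Nausea is mentioned once among the trial's own measurements. Section 3.3 says that staff will monitor the "need for the administration of other interventions to treat ketamine side effects (nausea etc". Section 5 has research staff collect adverse events under institutional policies, and section 4 compares adverse event rates between arms by Fisher's exact or chi-square test.

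**The concern.** The aim covers known side effects overall, in both incidence and severity. The instrument that carries the primary conclusion has no row for an effect that the protocol itself lists among the most common. Outside that instrument, nausea enters the data only through a decision to treat it or to report it. Mild or untreated nausea may leave no trace, and the protocol provides no severity grade or fixed time for the nausea that is recorded.

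What is at stake is the breadth of the final claim. The longer infusion could lower the dissociative items while leaving nausea unchanged or prolonging it, and the report could still speak of an overall reduction. It could equally reduce nausea, and that benefit might be missed. Section 1 hopes the slower infusion will widen ketamine's use as a non-opiate analgesic, so nausea bears on how the result would be applied.

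**Working it through.** The plan's own sample size comes first, because it shows what this point does not touch.

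1. Inputs from section 4: difference 1 unit, SD 1.2, two-sided alpha 5%, power 80%. Normal approximation: n per arm = 2 × (1.960 + 0.842)² × 1.2² / 1² = 2 × 7.85 × 1.44 = 22.6, rounded up to 23. The t-test version gives 23.6, rounded up to 24. The stated 24 per arm reproduces, and nothing in it depends on whether nausea is rated.

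2. Coverage, place by place:

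| Place | Nausea present? |
|---|---|
| Section 2, morphine comparison | Named among ketamine-arm effects |
| Section 2, 38-patient study | One of four most common effects |
| Section 2, complex regional pain review | First in the list of most common events |
| Section 3.3, monitored effects | No |
| Appendix A, SERSDA form | No |
| Section 3.3, Study Schedule (vital signs, SERSDA, VAS, RASS) | No row |
| Section 4, list of variables collected | Neither nausea nor anti-nausea treatment named |
| Section 3.3, interventions for side effects | Yes, as an example; no scale, times or analysis |
| Sections 4 and 5, adverse events | Not named; could be included if reported |

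The row "Generalized Discomfort" on the SERSDA form might absorb some nausea, but could not separate it from other discomfort.

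3. Size. The documents state no nausea rate for intravenous ketamine infusion alone, by duration or otherwise, so the number of unrecorded cases cannot be derived. Purely as arithmetic on assumed inputs: a rate of 10% to 25% is 24 × 0.10 = 2.4 to 24 × 0.25 = 6 subjects per arm, and if half went untreated, 1.2 to 3 per arm. Neither the rates nor the untreated half come from the documents, so this range is not evidence of size.

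4. What 24 per arm could show about nausea incidence, again at assumed rates. Normal-approximation power = Φ[(|p1 − p2|√n − 1.960√(2p̄(1 − p̄))) / √(p1(1 − p1) + p2(1 − p2))]. For 20% versus 10%: (0.10 × 4.899 − 1.960 × 0.505) / 0.500 = −1.00, giving 16%.

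| Assumed rates | Power, normal | Power, Fisher's exact | n per arm for 80% (normal) |
|---|---|---|---|
| 20% vs 10% | 16% | 10% | 199 |
| 30% vs 10% | 41% | 31% | 62 |
| 40% vs 20% | 32% | 24% | 82 |

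At these rates, neither the planned adverse event comparison nor an added rating could settle whether infusion time affects nausea.

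**The case against.** The strongest reply is that the primary outcome is internally consistent. It is defined by SERSDA, its nine items are listed directly after the objective, and the scale was built for dissociative effects. This stands: the trial can conclude on those items, and what remains is an aim worded more broadly than its measure.

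Second, nausea is not ignored. Treatment for it is monitored, adverse events are collected, and their rates are tested between arms. The institutional policies are not in the documents and may include grading. This also stands, which is why the point is limited to what the protocol specifies: no scheduled question and no severity scale.

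Third, the background is mixed. Section 2 describes minimal gastrointestinal effects at sub-dissociative doses, and reports nausea and vomiting in 7 morphine patients against 0 on subcutaneous ketamine. Section 1 names dizziness, unreality and mood changes, all SERSDA items. The 38-patient study offered rescue morphine, so its nausea cannot be put down to ketamine alone, and the review concerns complex regional pain. These facts weaken any claim about how frequent nausea will be. They do not change the fact that the protocol presents it as a known effect and uses it as its own example of a side effect needing treatment.

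Fourth, an added item would be underpowered, and ratings at 60 and 90 minutes may follow rescue fentanyl. Both are correct. They limit the item to description and favour the 30-minute rating, but a scheduled rating is still more informative than counts that depend on who treats or volunteers.

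**Conclusion.** The primary outcome is narrower than the stated aim, and nausea is captured only through treatment and adverse event reporting. This rests on the text alone and needs no assumption. The sample size, primary instrument and primary analysis are unaffected. The gain from a change is modest but cheap: scheduled severity data on one effect that the aim covers, descriptive only at 24 per arm under the assumed rates above.

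A reader might infer that the trial cannot conclude on side effects at all, or that nausea goes wholly unrecorded. The documents do not support either reading, given the SERSDA-based definition of the outcome, the monitoring of interventions and the planned comparison of adverse events. A reader might also infer that a known number of cases per arm would be missed. No figure in the documents supports such a count.

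**What to change.** Add one nausea/vomiting item to the bedside form, rated 0-4 at 0, 5, 15, 30, 60 and 90 minutes, and name it as a secondary descriptive outcome. Keep it out of the SERSDA score so that the primary outcome is unchanged. The time-0 rating is needed because abdominal and flank pain qualify for entry, so nausea may precede the infusion, and SERSDA itself is not scheduled at time 0. Take the 30-minute rating before any rescue medication is given at that visit and make it the main time point. Report the item by arm beside anti-nausea treatment use, which can itself lower later ratings, and beside the adverse event comparison in section 4. Word the primary conclusion as SERSDA-rated side effects.

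The cost is one question at existing bedside assessments, one REDCap field and a short amendment. Subjects already enrolled will have no rating, and there are too few patients for a powered nausea comparison. If enrolment is too far advanced for the item to be useful, the narrower wording of the conclusion can be adopted alone at no cost.

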If the patient meets all eligibility criteria, they will be consented by study staff members and then randomized to receive ketamine 0.25mg/kg in 100cc normal saline (NS), up to a

maximum of 30mg total dose, as an IV infusion over the specified time, as well as “placebo” 100cc NS over the other time slot.

[figure not shown]
If during the baseline assessment, immediately prior to the start of infusion, the subject reports an improved pain score (VAS < 5 cm(50mm)), the subject will be considered no longer eligible. The infusion will not be administered, and the subject will be removed from the study.

Since the subject was randomized, the group allocation (control or experimental group) for that subject will be reassigned to the randomization block to maintain a total of 48 enrolled (infused) subjects.

Pharmacy staff will provide the study medication in a blinded fashion to the nurse who will use infusion pumps to deliver both study medication and placebo simultaneously. Nursing staff will receive training on administration of the study medication prior to starting the study.

We will measure the side effect profile using the Side Effects Rating Scale for Dissociative Anesthetics (SERSDA) along with the Visual Analog Scale (VAS) (Appendix A).

Visual Analogue Scale scoring is done by asking the subject to mark the spot on the VAS Pain Assessment Tool (0-10cm) to indicate their perception of pain. Following this, the investigator scores the intensity of pain according to the 0-100mm corresponding scale (one instrument i.e., 5cm= 50mm). The VAS is a validated, subjective measure for acute and chronic pain. See below for exact tool that will be used.

Vital signs (heart rate, blood pressure, respiratory rate, and oxygen saturation) will also be obtained at 0, 5, 15, 30, 60, and 90 minutes from the start of the ketamine/NS placebo infusion.

Ketamine 30 min vs 15 min

Version: 7

Date: 06.06.2024

Page 7 of 15

Rescue Medication

At 30, 60 or 90 minutes post start of the ketamine infusion, if the study subject has a VAS score that is between 5-10cm (50-100mm), a **single** dose of both acetaminophen 1,000mg (oral) and ketorolac (15-30mg IV) will be given. If alternative medications are required, the study investigator will be consulted.

NOTE: EPIC recommends a ketorolac dose of 15mg IV if subject weight is less than 50kg or subject age is ≥ 65 years.

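### The plan has no between-arm criterion for the claim that analgesia is maintained: VAS ≤ 5 cm has no unit or test, and the mixed model has no 30-minute contrast, margin or confidence-interval rule

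*Combined protocol and SAP*

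**What the plan says.** Keeping analgesia is one of the two halves of the trial's hypothesis. Section 1 lists it as the second aim: "Maintain adequate pain control, as determined by a Visual Analogue Score (VAS) of ≤ 5 cm (50mm) at 30 minutes" after the start of the infusion. Section 3 (Study Design) frames it as a comparison: "The secondary outcome will be adequate pain control (VAS ≤ 5 cm(50mm)) and need for rescue analgesia between the two groups". Section 3.3 (Outcomes/Objectives) gives the objective: "The secondary objective is to ensure that adequate pain control (VAS ≤ 5 cm) is maintained when ketamine administration is prolonged". The same section names the secondary outcome measure as the 0-100 mm VAS at 30 minutes. It also says that, for a clinically significant reduction in pain, "there needs to be at least a 13mm difference on the 100mm VAS pain scale".

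For the analysis, section 4 says: "A mixed model regression will be employed for all continuous outcomes across time with missing data assumed to be random". It says nothing further about how VAS will be compared between arms. The sample size rests on the side-effect scale alone: "The sample size of n=24 in each study arm (n=48 overall) was determined to detect a clinically significant median change of one unit". The only other use of 13 mm is in section 5, where it defines improvement in the interim stopping rule, not a difference between arms.

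Under Rescue Medication in section 3, rescue is tied to the VAS reading "At 30, 60 or 90 minutes post start of the ketamine infusion", and data collection continues after rescue.

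**The concern.** To say that pain control is maintained when the infusion is lengthened is, once the arms are compared, to say that the longer infusion is not materially worse than the shorter one. That needs a stated tolerable loss and an interval that excludes it. The plan supplies neither.

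What it does supply cannot carry the claim.

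- **The threshold.** VAS ≤ 5 cm is not attached to a subject, an arm mean or a proportion. It has no target and no named test.
- **The model.** A mixed model across time yields several possible arm effects. The plan does not say which one answers the objective, although the outcome measure is fixed at 30 minutes.

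The intended message is fewer side effects with analgesia kept. Without a criterion, the second half of that message would rest on whatever the reader takes from the model output.

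**Working it through.** **1. The plan's own figure.** Inputs from section 4: difference 1 unit, SD 1.2 units, two-sided alpha 5%, power 80%. By the normal approximation, n per arm = 2 × (1.960 + 0.842)² × 1.2² / 1² = 22.6, so 23. The two-sample t-test gives 23.6, so 24, with power 80.7% at 24 per arm. The stated 24 per arm reproduces. It concerns SERSDA only; no VAS quantity enters it.

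**2. Does the 5 cm threshold settle the comparison?** No. For illustration, arm means of 30 mm and 45 mm at 30 minutes both lie at or below 50 mm, yet differ by 15 mm, which is more than 13 mm. Entry is also at VAS ≥ 5 cm (section 3.1), and the infusion is withheld only if the baseline reading is below 5 cm (section 3). A subject at exactly 5 cm therefore meets the success threshold before treatment.

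**3. What can 24 per arm show about VAS at 30 minutes?** The documents give no VAS SD, so 15 to 30 mm is assumed. The reference loss is 13 mm, and there is no baseline adjustment.

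- Standard error of the arm difference = SD × √(2/24).
- 95% CI half-width = t(0.975, 46) × SD × √(2/24) = 2.013 × 0.2887 × SD = 0.581 × SD.
- Chance that a true 13 mm loss is non-significant (two-sided 5%): noncentral t, 46 df, noncentrality 13/SE.
- Chance that the 95% CI excludes a 13 mm loss when the arms are equal (one-sided 2.5%): the same noncentral t, hence the complement of the previous line.
- n per arm for 80% power to exclude 13 mm = 2 × [(1.960 + 0.842) × SD / 13]², rounded up.

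| Assumed SD (mm) | SE (mm) | CI half-width (mm) | True 13 mm loss non-significant | 13 mm excluded if arms equal | n per arm for 80% |
|---|---|---|---|---|---|
| 15 | 4.33 | 8.7 | 16% | 84% | 21 |
| 16 | 4.62 | 9.3 | 21% | 79% | 24 |
| 20 | 5.77 | 11.6 | 40% | 60% | 38 |
| 25 | 7.22 | 14.5 | 58% | 42% | 59 |
| 30 | 8.66 | 17.4 | 69% | 31% | 84 |

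The half-width reaches 13 mm at SD = 13/0.581 = 22.4 mm. Above that, even an observed difference of zero does not exclude 13 mm. A result just short of significance has an upper limit of about twice the half-width, which passes 13 mm at SD = 13/(2 × 0.581) = 11.2 mm. Above that, a non-significant result can leave 13 mm inside the interval.

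**4. Effect of baseline adjustment.** Assuming a correlation of 0.5 between baseline and 30-minute VAS, the effective SD falls by the factor √(1 − 0.5²) = 0.866. The chance of excluding 13 mm then rises from 60%, 42% and 31% to about 72%, 53% and 40% at SD 20, 25 and 30 mm.

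**The case against.** Four arguments can be made for the plan.

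**An absolute criterion exists.** The objective ties maintained to VAS ≤ 5 cm, and section 1 defines adequate control that way. On this reading the aim is to reach a threshold, not to show non-inferiority. That is a fair reading of the words, but it does not rescue the plan. The threshold has no unit or test, and section 3 asks for a comparison between groups, which an absolute threshold does not answer.

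**The plan never says that non-significance will be read as maintained.** This is correct. A reader might infer it, because no other between-arm rule is stated, but no section says so. The point is that a claim rule is missing, not that a wrong one has been adopted.

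**Rescue does not clearly bias the result.** A reader might infer that rescue after the 30-minute reading pulls the arms together and makes a finding of no difference more likely. The documents do not establish this. The 30-minute VAS triggers the first protocol rescue and so precedes it. The plan does not say that an effect averaged over all times will be the test. The model also covers 5 and 15 minutes, before protocol rescue. By 15 minutes the control arm has had its whole dose and the experimental arm about half, so averaging could enlarge a difference. Rescue need is itself compared between arms. What stands is narrower: the 60- and 90-minute readings can follow rescue and should be interpreted that way.

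**The size is conditional, and 13 mm is not the plan's margin.** Both parts stand. At an SD of about 16 mm or less, 24 per arm gives roughly 80% power or more to exclude 13 mm, and baseline adjustment helps. Section 3.3 cites 13 mm for pain reduction, not as an acceptable loss between arms. Using it as a margin is a proposal that the sponsor would have to justify.

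**Conclusion.** The point holds as a missing criterion. The plan makes maintained analgesia part of its hypothesis and compares it between arms, yet gives no contrast, margin or interval rule by which that could be concluded. Neither attainment of VAS ≤ 5 cm in both arms nor a non-significant mixed-model result would show it.

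The absence of a rule is plain in the text and rests on no assumption. How much it matters depends on a VAS SD that the documents do not give, on 13 mm as the reference loss, and on all 24 subjects per arm contributing a 30-minute reading. At an SD near 15 mm the planned sample could usually support the claim if the arms are equal. From 20 mm upwards it often could not.

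The matter is secondary in rank, since the trial is sized on SERSDA, but it should be corrected before analysis because the trial's conclusion will lean on it.

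**What to change.** In section 4:

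- Name the arm difference in VAS at 30 minutes (30-minute infusion minus 15-minute infusion) as the secondary analysis. Take it from the mixed model as an arm-by-time contrast with baseline VAS as a covariate, and report it with a 95% CI.
- Pre-specify a margin and its justification. The protocol's own 13 mm is the natural candidate. Claim that analgesia is maintained only if the upper confidence limit is below the margin. Otherwise report the estimate and interval descriptively, without that claim.
- State that VAS ≤ 5 cm is applied per subject, and report the proportion meeting it at 30 minutes by arm, with a CI for the difference.
- Interpret VAS at 60 and 90 minutes as readings that can follow protocol rescue, alongside the rescue rates by arm.

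The cost is analysis-plan wording plus the work of justifying a margin; no extra data or subjects are needed. The downside is that, with 48 subjects, the trial may be unable to claim maintained analgesia.
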